4.3.4 Subgroups of interest

The following subgroups are of interest, based on patient characteristics at neratinib initiation (index date) or primary diagnosis of breast cancer. Analyses of primary, secondary, and exploratory outcomes may be performed for some or all of these subgroups, subject to pertinence and the number of patients in each subgroup.

1. Nodal status at initial diagnosis (0, 1-3, ≥ 4), Tumor size at initial diagnosis (T1, T2, \geq T3), Stage I vs Stage II+III
 - a. Low risk (Stage I and N- or pCR) vs high risk (Stage II/III or N+ or no pCR)
2. Previous adjuvant or neoadjuvant therapy (Yes/No)
3. Residual disease after neoadjuvant treatment (no pCR)
4. Prior trastuzumab-based regimen (trastuzumab only/ trastuzumab and pertuzumab/ T-DM1)

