4.2 Sample Size

Sample size calculation is not applicable, since the study plans to include all eligible breast cancer patients having received neratinib as an extended adjuvant therapy through the EAP in the target European countries. The number of patients is estimated to be up to 200 patients. Using the table below, the precision estimates for a 95% confidence interval (CI) were calculated around proportions ranging from 10% to 50% for a sample size between 150 and 300 patients (see Table 1).

A sample size of 200 patients would allow to assess a category of primary objective (demographic and clinical description of eligible patients) of 10%, 20%, 30%, 40% and 50% of patients with a precision of approximately $\pm 4.1\%$, $\pm 5.5\%$, $\pm 6.4\%$, $\pm 6.8\%$ and $\pm 6.9\%$, respectively.

Based on the feasibility, 120 patients would be enrolled instead of 200 patients originally planned.

A sample size of 120 or 100 patients would allow to assess a category of primary objective (demographic and clinical description of eligible patients) of 10%, 20%, 30%, 40% and 50% of patients with a precision of approximately $\pm 5.4\%$ or 5.9% , $\pm 7.2\%$ or 7.9% , $\pm 8.2\%$ or 9% , $\pm 8.8\%$ or 9.6% and $\pm 9\%$ or 9.8% , respectively.

Table 1 Precision estimates for 95% CI around proportions

Precision estimate*	Proportion				
	10%	20%	30%	40%	50%
Sample size	10%	20%	30%	40%	50%
100 patients	5.9%	7.9%	9%	9.6%	9.8%
120 patients	5.4%	7.2%	8.2%	8.8%	9%
150 patients	4.8%	6.4%	7.3%	7.8%	8.0%
200 patients	4.1%	5.5%	6.4%	6.8%	6.9%
250 patients	3.7%	4.9%	5.7%	6.1%	6.2%
300 patients	3.4%	4.5%	5.2%	5.5%	5.6%

*Precision estimates for a 95% CI were calculated using statistical analysis system (SAS) version 9.4 or higher (SAS Institute, Cary, NC, USA)

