7.10 Changes from Protocol

In the eCRF an additional inclusion criterium was considered, i.e., the patient was diagnosed with HER2+ breast cancer. For analysis proposes this additional criterium is considered in the analysis datasets and used in the identification of the FAS.

In the protocol the study entry date was defined as the cut-off date until when the eligible patients' data as obtained from medical charts are abstracted for analysis in the study. Based on a request from Pierre Fabre, the study entry date was assigned in the SAP to the date of first patient in, 05 July 2022, to ensure that all patients have the same cut-off date.

In section 8.2, two additional periods were considered in the time to event analysis, i.e., in protocol the intervals considered were 1, 3, 6, 9 and 12 and for analysis the periods that will be considered are 1, 3, 6, 9, 12, 15 and 18.

The subgroup analysis considered in section 8.4 has been updated from protocol. The nodal status at initial diagnosis and the tumor size at initial diagnosis were removed from the subgroups of interest. The subgroup previous adjuvant or neoadjuvant therapy was defined in the protocol as "Yes/ No" and will be updated to "Neoadjuvant + Post neoadjuvant treatment/ Adjuvant only".

The following subgroups analysis was added: according to EU label status, Concomitant Corrective Antidiarrheal, Concomitant Prophylaxis Antidiarrheal, Initial Dose of Neratinib.

In the protocol the exploratory analysis was planned to be performed only in HR+ patients, it will be analyzed separately for HR+ / HR- patients.

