8.4 Examination of Subgroups

The following subgroups are of interest, based on patient characteristics at neratinib initiation (index date) or primary diagnosis of breast cancer. Analyses of primary, secondary, and exploratory outcomes may be performed for some or all these subgroups, subject to pertinence and the number of patients in each subgroup:

- EU label status: Yes, No
 - Yes, defined as, HR+ patients with initiation of Neratinib ≤ 1 year from trastuzumab-based treatment completion in adjuvant setting (EU Label population)
 - No, otherwise
- Pathologic stage (AJCC classification) at primary breast cancer: Stage I, Stage II+III
 - If missing, derived as in 2
- Residual disease after neoadjuvant treatment (pathologic complete response [pCR]): pCR, No pCR

- Risk: Low risk (Stage I or N- or pCR), High risk (Stage II/III or N+ or no pCR)
 - N-, defined as, the electronic case report form (eCRF) nodal status category of NX or N0
 - N+, defined as $N \geq 1$ nodal
- Previous adjuvant or neoadjuvant therapy ⁽²⁾: Neoadjuvant + Post neoadjuvant treatment, Adjuvant only
 - Neoadjuvant + Post neoadjuvant, defined as, at least one neoadjuvant and one adjuvant treatment
 - Adjuvant only, defined as, at least one adjuvant treatment and no neoadjuvant
- Prior trastuzumab-based regimen overall (neoadjuvant or adjuvant): Trastuzumab only, Trastuzumab and Pertuzumab, Trastuzumab emtansine (T-DM1), Other anti HER2
- Prior trastuzumab based regimen the last treatment in adjuvant setting before Neratinib initiation: Trastuzumab only, Trastuzumab and Pertuzumab, Trastuzumab emtansine (T-DM1), Other anti HER2
- Hormone Receptor at Primary Breast Cancer Diagnosis: HR+, HR-
 - HR+, defined as either ER or PR or both are positive
 - HR-, defined as if ER and PR are negative
- Concomitant Corrective Antidiarrheal: Yes, No
- Concomitant Prophylaxis Antidiarrheal: Yes, No
- Initial Dose of Neratinib: <240mg, 240mg, >240mg

Table 2 AJCC staging

Primary tumor (T)	Regional lymph nodes (N)	Distant metastasis (M)	Stage
Tis	N0	M0	0
T1	N0	M0	IA
T0	N1	M0	IB
T1	N1	M0	IB
T0	N1	M0	IIA
T1	N1	M0	IIA
T2	N0	M0	IIA
T2	N1	M0	IIB
T3	N0	M0	IIB
T0	N2	M0	IIIA
T1	N2	M0	IIIA
T2	N2	M0	IIIA
T3	N1	M0	IIIA
T3	N2	M0	IIIA
T4	N0	M0	IIIB
T4	N1	M0	IIIB
T4	N2	M0	IIIB
Any T	N3	M0	IIIC
Any T	Any N	M1	IV

N2 and N3 are not collected in the CRF, this regional lymph node categories will be identified by “ ≥ 4 ” lymph nodes involved.

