10 PATIENT DISPOSITION

All patients with a signed informed consent, non-opposition, or ICF waiver will be accounted in this study. Patient disposition, withdrawals, including inclusion and exclusion criteria will be presented for all enrolled patients.

The following enrolment disposition variables will be described:

- Number and percentage of sites per country. Percentage computed among all active sites.
- Number and percentage of patients enrolled by site and country. Percentage computed among all patients enrolled in each country.

The following patient disposition characteristics will be described:

- Number of enrolled patients (ENR).
- Number and percentage of patients excluded from analysis by eligibility criteria not met. Percentage computed among ENR.
- Number and percentage of patients included in the analysis (FAS). Percentage computed among ENR.
 - Number and percentage of patients that withdrew consent. Percentage computed among FAS.
 - Number and percentage of patients lost to follow-up. Percentage computed among FAS.
 - Number and percentage of patients followed until end of observation period. Percentage computed among FAS.
 - Length of follow-up (months), calculated as:
 - $(EOB - Date\ of\ first\ neratinib\ administration + 1)/30.4$
 - Number and percentage of patients by survival status at study entry. Percentage computed among FAS.
 - If deceased, reason of death and occurrence during neratinib use. Percentage computed among FAS patients deceased at study entry.
 - Number and percentage of patients per analysis subgroup (section 8.4). Percentage computed among FAS.

- Number and percentage of patients included in the HR+ Analysis Set (HRAS). Percentage computed among FAS.

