11 PRIMARY OUTCOMES

The primary outcomes will be presented as frequencies and percentages or summary statistics, as appropriate, for the FAS and by subgroups (Section 8.4), subject to pertinence and the number of patients in each subgroup. No statistical testing will be carried out for primary outcomes.

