11.1 Demographic Characteristics at Neratinib initiation

To describe the demographic profile of the patients at neratinib initiation, the below demographic characteristics will be analyzed for FAS and by subgroup EU label; Pathologic stage; Residual disease after neoadjuvant treatment; Risk profile; Previous adjuvant or neoadjuvant therapy; Prior trastuzumab-based regimen overall and last treatment; and Hormone Receptor (Section 8.4):

- Age at neratinib initiation (years), calculated as:
 - *(Year of neratinib initiation – Year of birth)*
- Gender: Female, Male
 - Pregnancy: Yes, No, Unavailable
 - Breastfeeding: Yes, No, Unavailable
 - Menopausal status: Premenopausal, Perimenopausal, Postmenopausal, Surgical/other reason for amenorrhea, Unavailable
- Employment status: Full-time employment, Part-time employment, Student or pupil, Homemaker, Retired, Unemployed, Incapacity to work, Unavailable
- Weight (kg)
- Height (cm)
- Body mass index (BMI) (kg/m²), calculated as:
 - *Weight (kg)/ Height (m)²*

- BMI category [1]: Underweight ($< 18.5 \text{ kg/m}^2$), Normal weight ($18.5 - 24.9 \text{ kg/m}^2$), Pre-obesity ($25.0 - 29.9 \text{ kg/m}^2$), Obesity ($\geq 30.0 \text{ kg/m}^2$)

Weight changes after neratinib initiation are collected in the CRF, and will be analyzed as follows:

- Weight change from neratinib initiation, calculated as:
 - $(\text{Last available weight at neratinib stop date} - \text{Weight at neratinib initiation})$
- Number and percentage of patients by weight change: Weight gain, Weight loss, Weight stable
 - For weight gain and weight loss, the number and percentage of patients by percentage change will be presented: $<5\%$, $5\% \text{ to } 10\%$, $>10\%$.

The closest measurements to neratinib start and end date, respectively, will be used for the weight change calculation. For patients who might not have completed 1 year of Neratinib treatment the latest record of the weight under neratinib treatment will be considered. If the subject has neratinib ongoing at study end, the latest available measurement will be considered.

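### The SAP's Low and High risk groups overlap, section 8.4 gives no rule for patients who meet both, and the change from the protocol wording is not listed

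*SAP*

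**What the plan says.** SAP 8.4 gives the subgroup as "Risk: Low risk (Stage I or N- or pCR), High risk (Stage II/III or N+ or no pCR". Its sub-bullets define only the nodal terms: N- is NX or N0, and N+ is at least one node. There is no order of precedence.

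Protocol 4.3.4 has "Low risk (Stage I and N- or pCR) vs high risk (Stage II/III or N+ or no pCR". The High definition is the same. The Low definition joins stage and nodes with *and*, without brackets.

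SAP 7.10 states in general terms: "The subgroup analysis considered in section 8.4 has been updated from protocol". It then itemises changes: "The nodal status at initial diagnosis and the tumor size at initial diagnosis were removed from the subgroups of interest", a recoding of prior adjuvant/neoadjuvant therapy, and four added subgroups. The risk definition is not among them.

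The subgroup is used in several outputs. SAP 10 asks for "Number and percentage of patients per analysis subgroup (section 8.4). Percentage computed among FAS". SAP 11.1 has demographics "analyzed for FAS and by subgroup EU label; Pathologic stage; Residual disease after neoadjuvant treatment; Risk profile" and further subgroups. Sections 11.3, 12.1 and 12.3.1 also name the risk profile as a reporting subgroup.

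**The concern.** A two-level subgroup should place each classifiable patient in exactly one level. Here each level is an *or* of three criteria, and each criterion in one list is the opposite of a criterion in the other. A patient who is favourable on one and unfavourable on another therefore satisfies both.

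Two outcomes are possible. Either the rule is programmed literally, so the same patients sit in both risk columns and the disposition percentages total more than 100%, or the programmer chooses a precedence that nobody has recorded. In the second case, that choice decides who is reported as low risk.

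**Working it through.** The plan states no figure for the risk groups, so there is nothing to reproduce. The check is an enumeration.

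**Inputs.** Stage (I or II/III), nodes (N- or N+) and the Low and High rules come from SAP 8.4 and protocol 4.3.4. pCR status takes three values: pCR, no pCR, or no neoadjuvant therapy. I assume that a patient without neoadjuvant therapy meets neither pCR criterion. This gives 2 × 2 × 3 = 12 profiles. They are profiles, not patients, and are not equally common.

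**Step 1: SAP rule.**

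| Stage, nodes | pCR | no pCR | no neoadjuvant |
|---|---|---|---|
| I, N- | Low | **both** | Low |
| I, N+ | **both** | **both** | **both** |
| II/III, N- | **both** | **both** | **both** |
| II/III, N+ | **both** | High | High |

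Both = 1 + 3 + 3 + 1 = 8; Low only 2; High only 2; neither 0. Concrete cases are T2N0 (IIA in Table 2), T2N1 with pCR, and T1N0 without pCR.

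In Table 2, Stage I with N+ arises only through the IB rows, which need checking (step 5). Setting those three profiles aside leaves 8 - 3 = 5 of 9.

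**Step 2: protocol rule, both bracketings.**

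| Low rule | Both | Low only | High only | Both among pCR / no pCR / no neoadjuvant (4 each) | Both of 9, without I/N+ |
|---|---|---|---|---|---|
| SAP | 8 | 2 | 2 | 3 / 3 / 2 | 5 |
| (Stage I and N-) or pCR | 4 | 2 | 6 | 3 / 1 / 0 | 3 |
| Stage I and (N- or pCR) | 2 | 2 | 8 | 1 / 1 / 0 | 1 |

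The protocol wording also overlaps, but only for patients who had neoadjuvant therapy. For the others it is exclusive (0 of 4), and the SAP's *or* creates the overlap (2 of 4).

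**Step 3: effect on percentages.** No profile falls outside both groups, so with complete data

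Low% + High% = 100% + share in both.

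That share is not in the documents. SAP 4.2 gives the expected size: "Based on the feasibility, 120 patients would be enrolled instead of 200 patients originally planned". Assumed shares at 120:

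- 10%: 0.10 × 120 = 12 patients counted twice, total 110%
- 30%: 36 patients, total 130%
- 50%: 60 patients, total 150%

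A second illustration treats the inputs as independent, with assumed ranges of Stage I 20–40%, N+ 30–70%, neoadjuvant 30–60%, and pCR 30–50% of neoadjuvant patients:

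share = P(I,N-)·P(no pCR) + P(I,N+) + P(II/III,N-) + P(II/III,N+)·P(pCR).

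The lowest value is 0.06 × 0.21 + 0.14 + 0.24 + 0.56 × 0.09 = 0.443 (53 of 120). The highest is 0.14 × 0.30 + 0.06 + 0.56 + 0.24 × 0.30 = 0.734 (88 of 120). Stage depends on nodes, so independence is crude. The calculation shows only that the overlap need not be small.

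**Step 4: does the precedence matter?** Profiles placed in Low (of 12) under five exclusive rules:

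- High if any High criterion is met: 2
- Low = Stage I and (N- or pCR), rest High: 4
- pCR result decides for neoadjuvant patients, stage and nodes decide for the rest: 5
- Low = (Stage I and N-) or pCR, rest High: 6
- Low = the SAP's Low, rest High: 10

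Only 4 of 12 profiles keep the same label under all five: Stage I/N- with pCR or no neoadjuvant therapy (Low), and Stage II/III/N+ with no pCR or no neoadjuvant therapy (High).

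**Step 5: secondary query on Table 2.** This table supplies stage only when the recorded stage is missing. Its Stage I–III part has 17 rows but 15 distinct T/N pairs. T0N1 and T1N1 each appear under both IB and IIA, across the Stage I versus II+III cut. The variables in SAP 11.3 (NX/N0/N1 and node counts 0, 1–3, ≥4) do not separate them. The N2/N3 merge noted under the table stays within Stage III, so it does not cross the cut.

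**The case against.** The strongest counter-argument is that little depends on this variable. SAP 8.4 makes subgroup analyses optional, SAP 11 says "No statistical testing will be carried out for primary outcomes", and SAP 13.2 does not list risk among its time-to-event subgroups. Pathologic stage and pCR are shown as separate subgroups in 11.1, 11.3 and 12.1, so readers still have those components. This is correct and limits the severity. However, the study is descriptive throughout, so correctly formed columns are themselves the result. The disposition line in section 10 is not optional.

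Second, protocol 4.7.1 leaves subgroup detail to the SAP, and 7.10 openly says that the subgroups were updated. That also stands: the 7.10 point is a gap in documentation. Nor was the protocol rule clean, so restoring *and* would not be enough.

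Third, the table shells mentioned in SAP 9 were not available and might contain a rule. This cannot be excluded, but section 9 describes them as setting format and content. The definition belongs in 8.4.

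Fourth, the profile counts are unweighted and the patient shares are assumed. This is fair. The documents show that double counting can occur, not how often. The duplicate Table 2 rows may also be a qualifier lost when the PDF was read.

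**Conclusion.** The concern holds. Followed literally, the SAP's risk definition assigns 8 of 12 profiles (5 of 9 on the more cautious count) to both groups, against 4 or 2 of 12 under the protocol wording. No precedence is stated in the SAP text, and 7.10 does not itemise the change.

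The consequence is limited to the risk rows or columns of sections 10, 11.1, 11.3, 12.1 and 12.3.1. Overall results in the full analysis set and the HR+ set do not change. The number of patients counted twice is unknown; 12 to 60 of 120 corresponds to an assumed 10% to 50%. The profile counts assume that pCR status applies only after neoadjuvant therapy. This should be fixed, but it does not threaten the study's main findings. The Table 2 duplication is a query to check against the source, not an established error.

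**What to change.** - In SAP 8.4, define one risk group by explicit, bracketed criteria. Take the other as its complement among patients with the data needed, and show the rest as unclassified.
- The sponsor should state how pCR ranks against stage and nodes, because that decides the grouping. A plain rule of High if any High criterion is met would be exclusive, but it would remove pCR as a route to Low.
- Add the change from protocol 4.3.4 to SAP 7.10.
- Secondary: check Table 2 against its source. Give each T/N pair one stage, or set the derived stage to unknown where the collected data cannot resolve it.

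The cost is SAP wording, one entry in 7.10, and reprogramming of the risk variable (and of derived stage if Table 2 changes). No new data are needed. The number left unclassified cannot be told from the documents. The change should be made before database lock. The documents do not say whether lock has occurred; if it has, protocol 4.7.1 requires deviations from the SAP to be described in the study report or the statistical analysis report.

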9 OUTPUT PRESENTATIONS

The TLF shell templates provided with this SAP describe the presentations for this study and therefore the format and content of the summary TLFs to be provided by IQVIA RWS Biostatistics.

10 PATIENT DISPOSITION

All patients with a signed informed consent, non-opposition, or ICF waiver will be accounted in this study. Patient disposition, withdrawals, including inclusion and exclusion criteria will be presented for all enrolled patients.

The following enrolment disposition variables will be described:

- Number and percentage of sites per country. Percentage computed among all active sites.
- Number and percentage of patients enrolled by site and country. Percentage computed among all patients enrolled in each country.

The following patient disposition characteristics will be described:

- Number of enrolled patients (ENR).
- Number and percentage of patients excluded from analysis by eligibility criteria not met. Percentage computed among ENR.
- Number and percentage of patients included in the analysis (FAS). Percentage computed among ENR.
 - Number and percentage of patients that withdrew consent. Percentage computed among FAS.
 - Number and percentage of patients lost to follow-up. Percentage computed among FAS.
 - Number and percentage of patients followed until end of observation period. Percentage computed among FAS.
 - Length of follow-up (months), calculated as:
 - $(EOB - Date\ of\ first\ neratinib\ administration + 1)/30.4$
 - Number and percentage of patients by survival status at study entry. Percentage computed among FAS.
 - If deceased, reason of death and occurrence during neratinib use. Percentage computed among FAS patients deceased at study entry.
 - Number and percentage of patients per analysis subgroup (section 8.4). Percentage computed among FAS.

- Number and percentage of patients included in the HR+ Analysis Set (HRAS). Percentage computed among FAS.

11 PRIMARY OUTCOMES

The primary outcomes will be presented as frequencies and percentages or summary statistics, as appropriate, for the FAS and by subgroups (Section 8.4), subject to pertinence and the number of patients in each subgroup. No statistical testing will be carried out for primary outcomes.

11.1 Demographic Characteristics at Neratinib initiation

To describe the demographic profile of the patients at neratinib initiation, the below demographic characteristics will be analyzed for FAS and by subgroup EU label; Pathologic stage; Residual disease after neoadjuvant treatment; Risk profile; Previous adjuvant or neoadjuvant therapy; Prior trastuzumab-based regimen overall and last treatment; and Hormone Receptor (Section 8.4):

- Age at neratinib initiation (years), calculated as:
 - *(Year of neratinib initiation – Year of birth)*
- Gender: Female, Male
 - Pregnancy: Yes, No, Unavailable
 - Breastfeeding: Yes, No, Unavailable
 - Menopausal status: Premenopausal, Perimenopausal, Postmenopausal, Surgical/other reason for amenorrhea, Unavailable
- Employment status: Full-time employment, Part-time employment, Student or pupil, Homemaker, Retired, Unemployed, Incapacity to work, Unavailable
- Weight (kg)
- Height (cm)
- Body mass index (BMI) (kg/m²), calculated as:
 - *Weight (kg)/ Height (m)²*

- BMI category [1]: Underweight ($< 18.5 \text{ kg/m}^2$), Normal weight ($18.5 - 24.9 \text{ kg/m}^2$), Pre-obesity ($25.0 - 29.9 \text{ kg/m}^2$), Obesity ($\geq 30.0 \text{ kg/m}^2$)

Weight changes after neratinib initiation are collected in the CRF, and will be analyzed as follows:

- Weight change from neratinib initiation, calculated as:
 - $(\text{Last available weight at neratinib stop date} - \text{Weight at neratinib initiation})$
- Number and percentage of patients by weight change: Weight gain, Weight loss, Weight stable
 - For weight gain and weight loss, the number and percentage of patients by percentage change will be presented: $<5\%$, $5\% \text{ to } 10\%$, $>10\%$.

The closest measurements to neratinib start and end date, respectively, will be used for the weight change calculation. For patients who might not have completed 1 year of Neratinib treatment the latest record of the weight under neratinib treatment will be considered. If the subject has neratinib ongoing at study end, the latest available measurement will be considered.

11.2 Comorbidities

Relevant comorbidities prior to or ongoing at neratinib initiation are collected in the eCRF. The following variables will be analyzed for all comorbidities (prior to or ongoing at index date) and for comorbidities ongoing at index date, and presented for FAS:

- Number and percentage of patients with at least one relevant comorbidity. Percentage computed among FAS.
- Number of comorbidities per patient
- Comorbidities per patient category: 0, 1, >1 .
- Number and percentage of patients with each comorbidity present: Diabetes Type I, Diabetes Type II, Chronic kidney disease, Liver disease, Rheumatoid arthritis, Other chronic inflammatory disease, Heart disease, Heart failure, Arterial hypertension, Stroke, Arrhythmias, History of myocardial infarction, Depression, Lung cancer, Ovarian cancer, Uterine cancer, Colorectal cancer, Gastric cancer, Thyroid cancer, Melanoma, Sarcoma, Liver cancer, ENT

cancer, Acute myeloid leukemia, Previous breast cancer, Other cancer, Skin and subcutaneous tissue disorders, Autoimmune disorder, Gastrointestinal disorders, Other. Percentage computed among FAS.

Specified terms for Other cancer, Skin and subcutaneous tissue disorders, Autoimmune disorder, Gastrointestinal disorders and Other, will be coded using Medical Dictionary for Regulatory Activities (MedDRA) version 24.1 and will be described as number and percentage by System Organ Class (SOC) and Preferred Term (PT).

